## 6.6 Additional Analysis

### 6.6.1 Treatment Satisfaction Analyses

Investigator's global satisfaction with sarecycline treatment will be analyzed using data at Week 12 from a single question: "how satisfied are you with sarecycline treatment outcomes", with response options ranging from 'Very Satisfied' to 'Very Dissatisfied'. Frequency of responses will be tallied for all Subjects. Proportion of Subjects for whom Investigators indicated 'Very Satisfied' or 'Satisfied' will be reported.

The analyses will be done for the overall cohort, using FAS, and stratified by age and other relevant subgroups outlined in Section 6.3.2. Relationship between Investigator satisfaction and subject characteristics will be explored using descriptive analyses.

### 6.6.2 Treatment Compliance

Compliance will be assessed by comparing the expected number of tablets taken, based on the total number of treatment days between the encounters/surveys, with the number of used tablets identified/returned at each encounter/visit.

- The number of tablets expected to be taken/used for a specific treatment period between study encounters is calculated based on the number of treatment days in that period; if the

number of days is greater than 30, it will be set to 30, corresponding to the # of tablets in a single Seysara® bottle supplied to subjects during each study encounter/visit.

- The number of pills used for a specific treatment period between study encounters is calculated as a difference between 30 (maximum # of tablets in a Seysara® bottle dispensed for each study encounter) and # of unused/returned pills (by subject) at the following study encounter.

Compliance (%) for a given treatment/encounter period =  
[# of pills expected to be used - # of pills unused] \* 100 / [# of pills expected to be used]

Treatment compliance will be calculated for each subject/visit and over all study encounters/visits for the Safety population, as indicated above. For the overall compliance for each subject, average (mean) of % compliance at individual subject encounters/visits will be calculated.

Compliance values that are less than 0% will be set to 0%, and compliance values that are greater than 100% will be set to 100%. For Subjects with missing data, no missing data imputation will be performed, and the compliance statistics will be computed using non-missing values for the study cohort at relevant study timepoints.

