### 12.6.2 Treatment Compliance

Compliance will be assessed by comparing the expected number of doses taken, based on the total number of treatment days between the encounters/surveys and within the entire treatment period of the study, with the number of unused doses/tablets identified/returned at each encounter/visit. Treatment compliance will be calculated for each subject/visit and over all visits for the Safety population. Compliance values that are less than 0% will be set to 0%. Summaries will be presented using descriptive statistics for the Safety population.

$$\text{Compliance} = [\# \text{ Expected to be used} - \# \text{ Unused}] / [\# \text{ Expected to be used}]$$

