## 5.5 Compliance to Treatment

Compliance with the assigned treatment regimen was assessed by comparing the number of tablets expected to be used, based on the total number of treatment days, with the actual number used (expressed as a percentage of used/expected) at each encounter. The actual consumption/use of study tablets was evaluated by assessing the left-over pills/tablets in the medication bottles returned to sites/investigators by the Subjects.

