**Table 7.4.3. Seysara Treatment Compliance**

Average Compliance		
At Week 4 encounter		N, Mean % (SD) Median Min, Max
At Week 8 encounter		N, Mean % (SD) Median Min, Max
At Week 12 encounter		N, Mean % (SD) Median Min, Max

Compliance (%) for Week-4 encounter period =

$$[\# \text{ of pills expected to be used} - \# \text{ of pills unused}] * 100 / [\# \text{ of pills expected to be used}]$$

Compliance (%) for Week-4 encounter period =

$$[(AB2 - AB201) - (AA2 - AA201)] * 100 / [(AB2 - AB201)]$$

Compliance (%) for Week-8 encounter period =

$$[\# \text{ of pills expected to be used} - \# \text{ of pills unused}] * 100 / [\# \text{ of pills expected to be used}]$$

Compliance (%) for Week-8 encounter period =

$$[(R2 - R201) - (Q2 - Q201)] * 100 / [(R2 - R201)]$$

Compliance (%) for Week-12 encounter period =

$$[\# \text{ of pills expected to be used} - \# \text{ of pills unused}] * 100 / [\# \text{ of pills expected to be used}]$$

Compliance (%) for Week-12 encounter period =  
$$[(H2 - H201) - (G2 - G201)] *100 / [(H2 - H201)]$$

Note: Variables for "# of expected pills to be used" for each encounter needs to be calculated, and final Compliance % needs to be transformed, as outlined in Section 6.6.2.

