## 12.1 Appendix A: Study Schedule of Events

Study Encounter (physical or virtual)	Baseline E1	E2	E3	End of Study E4	Early Termination Visit
Week †		Wk 4 (± 4 d)	Wk 8 (± 4 d)	Wk 12 (± 4 d)	-
Informed consent	X				
Selection criteria	X				
Demographics & baseline clinical characteristics 	X				
Physical examination 	X			X	X
AV medical history and relevant comorbidites 	X			X	X
Seysara dose 	X	X	X	X	X
Dispensing and return of study medication	X	X	X	X	X
Prior acne medication (since diagnosis & past 6 months)	X				
Concomitant general medication	X			X	X
Concomitant anti acne medication	X			X	X
Site Investigator's clinical assessment of acne 	X	X	X	X	X
Study subject questionnaires 	X	X	X	X	X
AEs/SAEs 	X	X	X	X	X
Reasons for premature study withdrawal					X

† Expected in-person or virtual encounter/visit schedule, in relation to the index date (date of first administration of sarecycline).

 Clinical characteristics data assessed retrospectively based on what is documented in patient medical charts.

 Routine physical examination conducted as part of usual care alone and as documented in patient medical charts; such data may include - blood pressure, waist circumference, height/weight measurements.

 May include AV date of diagnosis, baseline severity, relevant comorbidities, per clinician judgment and/or as documented in patient medical charts immediately before the index date; new emerging comorbidities during the study period will be recorded, based on the documentation in patient medical charts.

 Expected usage is once daily, every day during the duration of the trial.

 Site Investigator assessments of AV severity of Subjects may be conducted during subject visit to clinician offices, or via remote/virtual (telehealth) visits owing to Covid-related travel restrictions.

 Subject self-assessments will include PtGA of acne severity; various HRQOL assessments will be conducted at baseline and Week 12.

 In the case of premature study discontinuation due to an AE, the Investigator should make every effort to collect the AE duration and outcome. Any SAE that is ongoing at the End of the Study or at the time of premature withdrawal will be followed up until the SAE is resolved or at least up to 4 weeks. AE follow-up information will be reported in the eDCF.

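### The compliance formula in SAP 6.6.2 counts tablets that were never due as missed, so a patient who takes every dose scores 92.9% over 28 days and 75.0% over 24 days

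*SAP*

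**What the plan says.** SAP 6.6.2 builds compliance from three pieces.

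- **Expected tablets.** These equal the treatment days in the period, with a ceiling: if the "number of days is greater than 30, it will be set to 30, corresponding to the # of tablets in a single Seysara® bottle".
- **Used tablets.** These are "calculated as a difference between 30 (maximum # of tablets in a Seysara® bottle dispensed for each study encounter) and # of unused/returned pills", so the unused count is what is left of a 30-tablet bottle.
- **Compliance.** The numerator is "of pills expected to be used - # of pills unused", divided by the expected count and multiplied by 100. Results below 0% are set to 0% and results above 100% are set to 100%. A patient's overall value is the mean of the period percentages.

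The shell of SAP Table 7.4.3 ("Seysara Treatment Compliance") repeats the verbal formula for Weeks 4, 8 and 12 and refers the programmer back to 6.6.2. Protocol 12.6.2 prints the same formula and compares the expected doses "with the number of unused doses/tablets identified/returned at each encounter/visit".

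SAP 5.5 describes a different quantity. It compares the expected tablets "with the actual number used (expressed as a percentage of used/expected) at each encounter". Protocol 8.5 also uses used over expected.

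**The concern.** The two counts in the numerator have different starting points. Expected tablets start from the days elapsed, and unused tablets start from a full bottle of 30. Unless the expected count is itself 30, their difference is not the number of tablets taken. The planned visit interval is four weeks, so the mismatch arises at the nominal schedule and grows when a visit falls early in its window.

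The result at stake is the compliance table for the Safety population. It would understate adherence by an amount set by the visit calendar, and two patients with the same behaviour would score differently because they attended on different days. Protocol 12.3.3 also names medication adherence as a possible covariate, and any such model would carry the same distortion.

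**Working it through.** The documents give no numerical compliance result, so there is no plan figure to reproduce. The check applies the SAP's own definitions.

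**Inputs**
- Bottle size: 30 tablets (SAP 6.6.2).
- Expected: E = min(d, 30), where d is the days in the period (SAP 6.6.2).
- Unused: U = 30 - tablets used (SAP 6.6.2).
- Dosing: "Expected usage is once daily, every day during the duration of the trial" (SAP Appendix A), so full adherence over d days, with d up to 30, means d tablets used.
- Visits at Weeks 4, 8 and 12, each +/- 4 days (Protocol 7). The first period can last 24 to 32 days. A gap between two later visits can last 28 - 8 = 20 to 28 + 8 = 36 days.

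**General form.** Substituting U = 30 - used:

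(E - U)/E = (E - 30 + used)/E = used/E - (30 - E)/E

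Before truncation, the printed formula is therefore used over expected minus a fixed penalty of (30 - E)/E. The penalty is 0 only when E = 30. With full adherence and d up to 30, the score is (d - (30 - d))/d = 2 - 30/d.

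**Full adherence**

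| Days d | E | U | Printed formula | Used/expected |
|---|---|---|---|---|
| 20 | 20 | 10 | 10/20 = 50.0% | 100% |
| 24 | 24 | 6 | 18/24 = 75.0% | 100% |
| 26 | 26 | 4 | 22/26 = 84.6% | 100% |
| 28 | 28 | 2 | 26/28 = 92.9% | 100% |
| 29 | 29 | 1 | 28/29 = 96.6% | 100% |
| 30 or more | 30 | 0 | 30/30 = 100% | 100% |

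**Partial adherence**
- 21 of 28 doses: U = 9, (28 - 9)/28 = 67.9%, against 21/28 = 75.0%.
- 18 of 24 doses: U = 12, (24 - 12)/24 = 50.0%, against 18/24 = 75.0%.
- 14 of 28 doses: U = 16, (28 - 16)/28 = 42.9%, against 14/28 = 50.0%.

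**The 100% cap.** Since U cannot be negative, (E - U)/E cannot exceed 100%, so the SAP's upper truncation can never act on the printed formula. Under used over expected it can: 30 tablets used in 28 days gives 30/28 = 107.1%. Under the printed formula the same patient has U = 0 and scores 28/28 = 100%, while the patient who used exactly the expected 28 scores 92.9%.

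**Overall score.** Three 28-day periods with full adherence average 92.9%. The latest in-window Week 12 visit is day 84 + 4 = 88, and three periods of 30 days need 90. At least one period is therefore shorter than 30 days, and no full adherer whose visits are all in window can reach 100% overall. Over all in-window schedules (whole days), a full adherer's mean runs from (75.0 + 100 + 50.0)/3 = 75.0%, for periods of 24, 36 and 20 days, to (100 + 96.6 + 96.6)/3 = 97.7%, for periods of 30, 29 and 29 days.

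**Cohort illustration (assumption: each visit day independent and uniform over its nine in-window days).** The mean scores for a fully adherent cohort are 90.88%, 88.89% and 88.89% for the three periods, and 268.66/3 = 89.55% overall. Used over expected gives 100%.

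**The case against.** The strongest reply concerns weight. Compliance is not a primary, secondary or listed additional endpoint. It is summarised descriptively, no analysis set or subgroup depends on it, and the SAP contains no multivariate section that would use adherence as a covariate. All of that stands. The endpoint and adverse-event results do not depend on this formula, and the covariate point applies only if the analysis allowed by Protocol 12.3.3 is actually run.

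The cohort mean depends on an assumed distribution of visit days. SAP 6.10 expects patients to miss or reschedule visits, and later visits shrink the bias, which is zero from 30 days on. The 50.0% case needs one visit at the late edge of its window followed by one at the early edge. The per-period arithmetic needs no such assumption. Nor do the documents set a compliance threshold, so no claim is made about patients falling below one.

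The right definition already appears in SAP 5.5, in Protocol 8.5 and in the used count of 6.6.2, and SAP Table 7.4.2 applies that count to treatment duration. This shows what was intended but does not cure the problem, because the explicit formula and the table shell do not use it. A patient who takes 28 tablets in 28 days would be credited with 28 treatment days in Table 7.4.2 and 92.9% compliance in Table 7.4.3.

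The formula would be correct if unused meant missed doses, but the SAP equates it with returned tablets. Protocol 12.6.2 does not mention a 30-tablet bottle, and if supply equalled the expected count its formula would be right. The error arises once the SAP adds the bottle size. The variable names in Table 7.4.3 are not defined, so only its verbal formula can be judged.

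**Conclusion.** The formula is wrong as written. In every period shorter than 30 days it understates compliance by (30 - E)/E before truncation: 2/28 = 7.1 percentage points at 28 days, 6/24 = 25.0 at 24 and 10/20 = 50.0 at 20. There is no error when the expected count is 30.

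This rests on the SAP's constant of 30 tablets per bottle, on once-daily use, and on all leftover tablets being returned and counted. The consequence is confined to the compliance table and any later use of those values. It should still be corrected before the table is programmed, because the error is present at the nominal visit interval and always runs in the same direction.

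**What to change.** In SAP 6.6.2 and in the verbal formulas of Table 7.4.3, replace the calculation with:

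Compliance (%) = (30 - number of unused tablets) x 100 / number of expected tablets

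Keep the truncation at 0% and 100%; the upper limit then has a purpose. In the variable-level formulas of Table 7.4.3, define each variable and make the numerator tablets dispensed minus tablets returned. Align Protocol 12.6.2 as (dispensed - returned)/expected, since it gives no bottle size, so that it agrees with Protocol 8.5 and SAP 5.5.

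The cost is one formula in SAP 6.6.2, its three verbal and three variable-level repeats in Table 7.4.3, and a wording change in the protocol. The returned-tablet counts are already collected, so no new data are needed.

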**Table 7.4.2. PROSES Study Duration & Seysara Treatment Duration**

	Total
Cumulative study duration, n (%) a	
Day 1 (all)	300 (100%)
≥ 4 Weeks 	N (%)
≥ 8 Weeks 	N (%)
= 12 Weeks 	N (%)
Cumulative treatment duration, n (%) a	
Day 1 (all)	300 (100%)
≥ 4 Weeks 	N (%)
≥ 8 Weeks 	N (%)
= 12 Weeks 	N (%)
Treatment duration (days) b	N
	Mean (SD)
	Median
	Min, Max

N = number of subjects in the safety population; n = number of subjects within a specific Category.

aDistribution categories were cumulative; subjects were included in each category for which they qualified.

bTreatment duration is the total number of pills used across each treatment period between study encounters. Number of pills used for each encounter is calculated as a difference between 30 (maximum # of tablets in a Seysara® bottle dispensed for each study encounter) and # of unused/returned pills (by subject) at the following study encounter.

XX patients discontinued before week-4 encounter.

XX patients discontinued between week-4 and week-8 encounter.

XX patients discontinued between week-8 and week-12 encounter.

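### The SAP compliance formula counts surplus tablets from a 30-tablet bottle as missed doses, so a patient who misses none scores 92.9% over the nominal 28 days

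*SAP*

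**What the plan says.** SAP 6.6.2 builds compliance for each interval between encounters from three quantities.

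- Expected tablets: the treatment days in the interval, with a cap: if the "number of days is greater than 30, it will be set to 30, corresponding to the # of tablets in a single Seysara® bottle".
- Used tablets: "calculated as a difference between 30 (maximum # of tablets in a Seysara® bottle dispensed for each study encounter) and # of unused/returned pills".
- Compliance: the numerator is "of pills expected to be used - # of pills unused", multiplied by 100 and divided by expected.

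The opening sentence of the section says that expected tablets are compared "with the number of used tablets identified/returned at each encounter/visit". Negative values become zero, and "compliance values that are greater than 100% will be set to 100"%. For each subject's overall figure, the "average (mean) of % compliance at individual subject encounters/visits will be calculated".

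Table 7.4.3 repeats the same verbal formula for the Week 4, Week 8 and Week 12 intervals. It adds a line of coded variables for each, which the documents do not define, and sends the programmer back to 6.6.2 for the final transformation.

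SAP 5.5 describes the comparison differently: expected tablets against "the actual number used (expressed as a percentage of used/expected) at each encounter". Protocol 8.5 agrees with it. Footnote b of SAP Table 7.4.2 also uses the dispensed count: "Number of pills used for each encounter is calculated as a difference between 30" and the tablets returned. Protocol 12.6.2 prints the same form of numerator as SAP 6.6.2, but the protocol never says how many tablets a bottle holds.

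**The concern.** Subtracting leftovers from expected tablets is right only if the patient was given exactly the expected number. Here the bottle holds 30 tablets and the planned interval is four weeks. A patient who takes one tablet every day for 28 days hands back two, and the formula treats those two as doses that should have been taken. SAP 6.6.2 defines the quantity that would avoid this, tablets used, and then leaves it out of the formula.

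The compliance figure would then partly measure how early patients came back to the clinic. A reader of Table 7.4.3 would see adherence below 100% in people who missed nothing, beside a Table 7.4.2 that counts every one of their tablets as used.

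**Working it through.** **Inputs.** One tablet daily (Appendix A, footnote 4, in both documents). One 30-tablet bottle per interval (SAP 6.6.2). Nominal interval four weeks, d = 28 days (protocol 7.3 and 7.4). Each visit has a window of ±4 days (protocol section 7 and Appendix A). The plan states no compliance result, so there is no figure to reproduce.

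**Interval lengths within the windows.** First: 28 − 4 = 24 to 28 + 4 = 32 days, counting from the first dose as in protocol section 7. Second and third: shortest (56 − 4) − (28 + 4) = 20 days, longest (56 + 4) − (28 − 4) = 36 days.

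**Formulas.** Let u be the tablets returned and e = min(d, 30).

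- As printed: 100 × (e − u)/e.
- Used over expected, with the SAP's own definitions: 100 × (30 − u)/e.
- Difference before limits: (30 − e)/e, which is (30 − d)/d for d < 30 and zero from 30 days on.

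**No missed dose**, so u = 30 − d up to 30 days:

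| Days d | Returned u | As printed | Used/expected |
|---|---|---|---|
| 20 | 10 | (20 − 10)/20 = 50.0% | 20/20 = 100% |
| 24 | 6 | (24 − 6)/24 = 75.0% | 24/24 = 100% |
| 26 | 4 | (26 − 4)/26 = 84.6% | 26/26 = 100% |
| 28 | 2 | (28 − 2)/28 = 92.9% | 28/28 = 100% |
| 29 | 1 | (29 − 1)/29 = 96.6% | 29/29 = 100% |
| 30 | 0 | 30/30 = 100% | 30/30 = 100% |

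**Missed doses.** Two missed in 28 days means u = 4: printed 24/28 = 85.7%, used/expected 26/28 = 92.9%. The gap is again 2/28 = 7.1 points.

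**Where the limits change the gap.** At 28 days with u = 1: printed 27/28 = 96.4%; used/expected 29/28 = 103.6%, cut to 100%; gap 3.6 points. At 28 days with u = 0: both give 100%, since 30/28 = 107.1% is cut; gap zero. The upper limit bites only when fewer than 30 − d tablets come back. The lower limit bites when u exceeds d. If treatment days are counted to discontinuation, a patient who stops at day 15 with no missed dose scores (15 − 15)/15 = 0%.

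**Ordering.** Two doses missed over 30 days: (30 − 2)/30 = 93.3%. None missed over 28 days: 92.9%. The less adherent patient ranks higher.

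**Per-subject mean.** Three 28-day intervals with no missed dose: 92.9%, while the Table 7.4.2 method counts 3 × 28 = 84 tablets over the same 84 days. Intervals of 24, 28 and 28 days: (75.0 + 92.9 + 92.9)/3 = 86.9%.

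**Range for a cohort.** The documents give no distribution of visit days. Assume, for range only, that visit days are independent and uniform over ±4, ±2, ±1 or 0 days, and that every available tablet is taken. The printed formula then averages 89.6%, 92.1%, 92.7% and 92.9%. Used/expected with the cap at 30 gives 100% throughout.

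**The case against.** The numerator comes from protocol 12.6.2, so the SAP follows its protocol. That is true, but the protocol names no bottle size. The SAP introduced the 30-tablet bottle, and with it the mismatch. Nor can unused be read as missed doses, because SAP 6.6.2 equates it with the tablets returned.

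The coded variables in Table 7.4.3 are undefined, so what would be programmed is not fully certain. This limits certainty about the code, but the words beside the variables repeat the formula of 6.6.2.

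The 20-day case is a corner: one visit four days late and the next four days early. Under the uniform ±4-day assumption it is 1 of 81 later intervals, and it cannot occur in the first. The nominal 28-day case does not depend on it.

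The error lowers compliance, so it does not flatter the product, and Table 7.4.2 reports tablets used separately. Both stand and bear on importance, not correctness.

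Three stronger readings are tempting. A reader might infer that every interval under 30 days loses the full (30 − d)/d. It does not: with the limits the loss can be smaller, and it is zero for an empty bottle. A reader might call the upper limit of 100% a contradiction. It is only redundant, because the printed formula can reach 100% but not exceed it; the limit does suggest that used over expected was intended. A reader might also count the cap at 30 as part of the error, since an empty bottle after 32 or 36 days scores 100% although at least 2 or 6 days had no supply. The SAP states the cap and ties it to the tablets supplied, so it is a debatable choice separate from this mistake.

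**Conclusion.** The formula is wrong as written and conflicts with SAP 5.5, with protocol 8.5 and with the used-tablet definition in its own section. A patient with no missed dose is under-scored by 7.1 points at the nominal 28 days, 25.0 at 24 days and 50.0 at the 20-day extreme. Nothing elsewhere in the documents repairs it.

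These figures rest on one tablet daily, a full 30-tablet bottle at each dispensing and leftovers returned. The first-interval range also assumes that days run from the first dose; SAP section 4 instead ties the index date to prescription. SAP 6.10 expects missed and rescheduled visits, so actual intervals may fall outside the windows.

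The consequence is limited to the descriptive summary in the Safety population: Table 7.4.3 and the per-subject mean. A reader might infer that the effectiveness results are affected, since protocol 12.3.3 mentions adherence as a possible adjustment variable. The SAP specifies no such model, and none of its endpoint analyses uses compliance.

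**What to change.** In SAP 6.6.2 and in all three formulas of Table 7.4.3, use:

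compliance (%) = (30 − # unused) × 100 / min(treatment days, 30), limited to 0–100%.

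Add a sentence saying that this departs from the formula in protocol 12.6.2 because bottles hold 30 tablets. Keep the cap at 30. Reporting how many intervals exceeded 30 days is optional, but it would let a reader see where supply could have run out.

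The cost is one formula. Pill counts and encounter dates are already collected. Reported compliance will rise for intervals under 30 days unless the bottle came back empty, and will not change from 30 days on. The 100% limit then does real work: an empty bottle after 28 days gives 107.1% and is set to 100%.
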